## 1. Study Protocol

### 1.1 Study aims and design

This study, sponsored by the National Institute of Diabetes and Digestive and Kidney Diseases (NIDDK), aims to optimize online behavioral lifestyle intervention (BLI) by testing whether any of five theory-driven experimental intervention components increase the proportion of individuals achieving a minimum clinically significant weight loss of  $\geq 5\%$  of initial body weight and/or mean weight loss after 12 months of treatment. The rationale and design of the study methods are informed by the 3-Phase Multiphase Optimization Strategy (MOST) framework. Per the MOST Optimization Phase, a factorial experiment will be conducted to determine which, if any, of the experimental intervention components contributes to improved treatment outcomes. Adults with a body mass index (BMI) in the overweight or moderately obese range ( $25-30 \text{ kg/m}^2$ ) will receive the preexisting 12-month Rx Weight Loss (RxWL) and a random combination of 0-5 of the experimental intervention components. A priori optimization criteria will be used to evaluate which, if any, of the experimental intervention components should be included in an optimized RxWL treatment package, which can then be tested in a future randomized controlled trial per the MOST Evaluation Phase. Mediation analysis will also be conducted to determine whether the experimental intervention components exerted their intended effects on their putative behavioral and psychosocial mechanisms, and whether those effects were associated with improved weight loss outcomes. Moderators analysis will explore for whom and under what circumstances the experimental intervention components might have been more or less effective. Assessments of weight and hypothesized mediators will occur at baseline and 3, 6, and 12 months after randomization. The study aims are:

**1.1.1 Aim 1:** Optimize RxWL via a factorial experiment to determine which combination of intervention components maximizes the proportion of participants achieving a  $\geq 5\%$  weight loss and mean weight loss at 12-months.

**1.1.2 Aim 2:** Conduct mediation analysis using proximal outcomes to test hypothesized mechanisms of action and moderator analysis to understand for whom and under what circumstances the interventions are effective.

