## 1.6 Statistical Analysis Plan

**1.6.1 Analytic plan.** Statistical analysis will follow good practices for the evaluation of randomized controlled trials as embodied in the CONSORT statement. Missing data will be imputed using a multiple imputation approach and outcome models averaged across imputations to adhere to the intent-to-treat principle. We will compare the sensitivity of the findings to alternative methods for handling missing data (see Missing Data Section below).

As a preliminary step, demographics, baseline weight and health history will be summarized across the aggregate sample and compared between cells (intervention components) using Analysis of Variance (ANOVA) for continuous variables, chi-squared analyses for categorical variables and non-parametric tests as appropriate. Variables will be considered potential confounders in the subsequent models if these variables are correlated with the outcome under consideration (at a modest  $p < .30$  level). The distribution of each of study outcome will be assessed using both parametric and graphical methods and transformed as necessary (e.g. log transform towards normality). Potential distributions for the outcome variables

include normal and binomial, and zero-inflated distributions.

Evaluation of the intervention components will involve generalized linear models that regress percent weight change from baseline (e.g., normal distribution & identity link function) and achievement of a  $\geq 5\%$  weight loss (binomial distribution & logit link function) on effect-coded indicators for each of the five intervention components and unique 2 through 5-way interactions of components. Effect coding  $(-1,1)$  is essential in analyzing factorial designs and results in regression weights that correspond to main effects and interactions.

Effect-coded main effects and interactions are orthogonal to one another, yielding unbiased estimation of standard errors, and equal power for main effects and interactions for given effect sizes. Using this approach, individual cell sizes (for each combination of components) does not limit statistical power. Models will adjust for confounders identified during preliminary analyses, including demographics, health and weight history that are associated with weight loss outcomes.

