**1.6.3 Sample size and power estimates.** Following the full factorial design, each of the planned 384 participants is randomly assigned to each of the five intervention components. There are 32 possible combinations of intervention components, but each component will be administered to 192 persons and withheld from 192 persons. Using the generic approach described by Lehr, a sample size of  $n = 192$  per group permits the detection of standardized effect sizes (SEs) of  $\Delta = (4/n^{.5})$  (where 4 encompasses standard assumptions of a type-I and type-II error rate of  $\alpha = .05$  and  $\beta = 20\%$ , respectively where  $4 \approx \sqrt{2} \times (|z\alpha/2 + z\beta|)$ , and solves to  $SE = 0.29$ ). According to estimates based on our preliminary data, RxWL without additional intervention components produces  $\geq 5\%$  weight loss for 50% of the sample, and the standard deviation on percent weight change will be 5.8% at 12-months. This generic approach estimates power to detect intervention component effects of 9% on proportion achieving  $\geq 5\%$  weight loss and effects of 1.7% on mean weight loss. Statistical power was further evaluated using Monte Carlo estimation, the model specification (with effect coding) for the proposed study, and parameter estimates based on previous RxWL trials. This tailored approach yielded estimates of 91% power to detect a component marginal effect size of  $ES = 0.16$  or an additional 3% achieving  $\geq 5\%$  weight loss and just under 1% additional weight loss due to component effects. The study is adequately powered because a lesser effect would not be clinically significant.

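### At N=384, 91% power cannot go with an effect of 0.16, a 3-point gain and just under 1% of weight; the 3 points fails on either scale at the stated 50% rate

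*Combined protocol and SAP*

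**What the plan says.** Section 1.6.3 makes two power statements for the same 384 participants, with each component given to 192 and withheld from 192.

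- **Generic formula.** At two-sided 5% and 80% power, the detectable standardised effect is 0.29, or 1.7% on mean weight loss. On the binary outcome: "This generic approach estimates power to detect intervention component effects of 9% on proportion achieving" at least 5% loss. The section gives 50% reaching 5% loss without extra components, and an SD of 5.8% for percent weight change.
- **Simulation.** Power was then re-estimated by Monte Carlo, using "the model specification (with effect coding) for the proposed study, and parameter estimates based on previous RxWL trials". The result is reported as follows: "This tailored approach yielded estimates of 91% power to detect a component marginal effect size of" 0.16. The sentence equates this with a further 3% of participants achieving at least 5% "weight loss and just under 1% additional weight loss due to component effects".

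The section concludes: "The study is adequately powered because a lesser effect would not be clinically significant".

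Section 1.6.1 specifies (-1,1) effect coding, which it says "is essential in analyzing factorial designs and results in regression weights that correspond to main effects and interactions". Section 1.6.3 does not say whether 0.16, 3% and just under 1% are such regression weights or differences between participants with and without a component.

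**The concern.** The second statement claims higher power (91% against 80%) for about half the effect (0.16 against 0.29) in the same sample. That needs either a large reduction in residual variance, which is not reported, or a change of scale, which is not stated.

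The closing sentence treats 3 points and just under 1% of weight as the smallest effects that matter, and claims the study can detect them. If it cannot, a null result for a component would be read as good evidence against a worthwhile effect when the design would usually miss one of that size. The proportion reaching 5% loss is the first-named outcome of Aim 1, which is to "determine which combination of intervention components maximizes the proportion of participants achieving a" loss of at least 5%. Nothing is claimed here about which components would be selected, because the optimization criteria in section 1.1 are not specified.

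**Working it through.** **Inputs from the plan.** N = 384 (1.4.3); 192 on and 192 off, two-sided 5% through z(α/2), 50% base rate, SD 5.8% (1.6.3); (-1,1) coding (1.6.1).

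**Assumptions.** The simulation's alpha, covariate R² and base rate are not given. I take two-sided 5%, R² of 0, 0.10 and 0.20, and no attrition, which is the most favourable case.

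**1. The generic mean figure reproduces.** 4/√192 = 0.289, and 0.289 × 5.8 = 1.67%. Noncentral t power at 0.29 SD is 80.9%.

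**2. Reading A: 0.16 is the on-minus-off difference.** This is 0.16 × 5.8 = 0.93% of weight, matching just under 1%. The noncentrality is d√(n/2) = 0.16 × √96 = 1.57, giving 34.6% power. Covariates turn d into d/√(1 − R²): power is 38% at R² = 0.10 and 42% at 0.20. Power of 91% needs d = 0.338, so R² would have to be 1 − (0.16/0.338)² = 0.78.

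**3. Reading B: 0.16 is the (-1,1) weight.** The weight is half the on-minus-off difference, so the difference is 0.32 SD. The noncentrality is 0.32 × √96 = 3.14, giving about 88% power; R² = 0.10 gives 90.9% and 0.20 gives 93.8%. The 91% is then plausible, but the component effect is 0.32 × 5.8 = 1.86% of weight.

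The interaction terms do not change this. Simulating the full 32-term model with 12 per cell (20,000 runs) gave 34.8% for Reading A and 87.6% for Reading B, or 91.2% for Reading B with R² = 0.10.

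**4. The 3 points.** With s₀ = √(2p̄(1 − p̄)/n) and s₁ = √((p₁q₁ + p₂q₂)/n), power is Φ[(Δ − 1.96s₀)/s₁] plus the opposite tail. For 50% v 53%, s₀ and s₁ are both 0.0510, so Φ[(0.03 − 0.100)/0.0510] = 0.085; adding 0.005 gives 9.0%.

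| Comparison | Two-sided 5% power |
|---|---|
| 50% v 53% (3 points) | 9.0% |
| 47% v 53% (3 doubled to 6) | 21.7% |
| 3 points from a base of 10% or 87% | 15% |
| 3 points from a base of 2% | 36% |
| Logit weight 0.16 (46% v 54%) | 35% |

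One-sided, 3 and 6 points from 50% have 14.5% and 32.0%. Six points comes near 91% only at extreme base rates: from 1% or 93% it has 85% two-sided and 91.5% one-sided.

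**5. The three effects against each other.** Assuming a normal outcome with half reaching 5% loss, a 0.16 SD shift moves Φ(0.16) − 0.5 = 6.4 points. Three points is Φ⁻¹(0.53) = 0.075 SD, or 0.075 × 5.8 = 0.44% of weight.

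**6. The generic 9 points.** 50% v 59% has 42.5% power (42.8% with unpooled variance). A difference of 14.1 points is needed for 80%. The plan's own formula agrees: 0.289 × √(0.5 × 0.5) = 14.4 points.

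**7. What the design can detect.** Power of 91% needs 0.338 SD (0.338 × 5.8 = 1.96% of weight) or 16.5 points from 50%. At a 1.0% difference (1/5.8 = 0.172 SD) power is 39.2%.

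**The case against.** The best defence is Reading B. The simulation used effect coding, and section 1.6.1 describes the regression weights as main effects. On that scale 0.16 × 5.8 = 0.93%, so 0.16, just under 1% and roughly 91% agree for the mean outcome. The plan also says "Models will adjust for confounders identified during preliminary analyses, including demographics, health and weight history that are associated with weight loss outcomes", so some gain from adjustment is expected. On this view the mean-outcome problem is an unlabelled scale, not a shortfall in power.

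Part of this stands. The simulation inputs are unknown, so the source of the mismatch cannot be identified and 91% for the mean should not be called impossible. But the plan describes the effect as additional loss due to a component. A reader takes that as the difference between having and not having the component, and on Reading B that difference is about 1.9%. The description is then wrong instead of the power.

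Reading B does not rescue the 3 points, which doubled still has only 22% power. Extreme base rates combined with a one-sided test could, but they contradict the stated 50% and the two-sided formula.

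Two further points are fair. Step 5 rests on a normal outcome and is supporting evidence only. The generic 9 points is a separate error that says nothing about the simulation.

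**Conclusion.** The concern holds. Either the 91% or the effect description is wrong for mean weight loss: about 35% power if just under 1% is the component's effect, or a component effect of about 1.9% if the power is near 91%. For the proportion reaching 5% loss, 3 points has 9% power from 50%, or 22% if doubled, so the claim fails on both scales. The generic 9 points has 42-43% power, not 80%.

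The statement that the study is adequately powered therefore does not follow from the plan's own figures, and the shortfall is largest for the first-named outcome of Aim 1. The calculations assume 192 versus 192, two-sided 5% and no attrition. The R² values are assumptions, and none tried (up to 0.20) takes Reading A above 42%.

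**What to change.** In section 1.6.3:

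1. State whether 0.16 is a (-1,1) weight or an on-minus-off difference.
2. Give all detectable effects as on-minus-off differences. Unadjusted and without attrition these are 0.29 SD (1.7% of weight) or about 14 points from 50% at 80% power, and about 0.34 SD (2.0% of weight) or about 16.5 points at 91%.
3. Correct the generic 9% to about 14 points.
4. If the simulation figure is kept, report its alpha, R² and base rate, and give its effect as a difference (0.32 SD, about 1.9% of weight, if 0.16 is the weight).
5. Remove 3% as an effect with 91% power.
6. Remove or revise the closing adequacy sentence, stating that unadjusted power is about 39% for a 1% on-minus-off difference and about 9% for 3 points. Both figures hold whichever scale 0.16 is on.

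The cost is wording only. The stated sensitivity becomes less favourable; the sample size, design and models do not change.
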